4.5.4 Drug Accountability

The NIH CC Pharmacy is responsible for the accountability of all unused investigational product. Adequate drug accountability records include documentation of all investigational products and supplies shipped, received, prepared and dispensed by the NIH CC Pharmacy. Participants will be asked to complete an eye drop diary documenting the number of drops as well as the days and times the investigational product was administered. At each applicable visit, participants will return the eye drop diary, unused investigational product and used investigational product dropperettes in the disposal container. The investigator/study staff will review the eye drop diary with the participant for completeness and accuracy and document the number of returned dropperettes (both used and unused). Missed doses of investigational product and incorrect doses below the prescribed amount will be documented in the eye drop diary but will not be reported to the IRB as protocol deviations. The study staff will dispose of returned investigational product dropperettes in the hazardous waste disposal bins.

4.5.5 Concomitant Medications and Treatments

Attempts at treating the macular cystic changes in retinal degenerations with CAIs [e.g., Acetazolamide (Diamox) or topical Dorzolamide (Trusopt)] have had variable success. The half-life of the systemic Acetazolamide is 3-9 hours and a rebound effect has been

described. If the potential participant receiving IP is using a CAI at the time of screening, s/he will be asked to continue using the medication at the same dosage during the study. The investigator should only initiate changes to the participant's CAI regimen for safety reasons. The effect of the addition of IFN gamma-1b on recalcitrant macular cystic changes will be assessed.

4.6 Follow-up/Termination Procedures

At the conclusion of the study, the participants will no longer be able to be seen under this protocol. Follow-up care will be arranged with an outside ophthalmologist or the participant will continue to be seen at the NIH under another protocol, if available and the participant is eligible. The participants and their physicians, with written consent, will be informed of the participant's disease status during this study. Clinical data obtained during participation will be shared with the participants and their private physicians (with written permission from the participant). Results from the overall study will be shared once the study team has analyzed the data from all participants.

4.7 Storage of Samples and Data

Skin biopsy and blood samples to develop fibroblast and lymphoblast cell lines that will be used to develop stem cells may be stored. Personal identifiers will be removed from samples prior to processing and all samples will be coded. After processing, specimens will be stored in freezers in secured buildings on the NIH campus. The manipulation of somatic cells may include the propagation, creation, and study of iPSCs, as well as the establishment of *in vitro* cultures. Cells may be genetically altered in the laboratory for experimental purposes and may be used for *in vivo* research. No cells, tissue or other sample components will be used for reproduction, cloning, or growth of new organisms.

Research samples may be stored for future use at the NEI as specified in the informed consent document. The participant has a choice to limit sample usage by selecting one of the following consent options:

Your data and samples may be used for other research projects, including those not related to retinal diseases, if you agree. Please initial on the line below that reflects your choice:

_____ *YES. You may use my data and samples for other research projects, including those not related to retinal diseases.*

_____ *NO. I do not want my data and samples used for other research projects. Please destroy my samples once this project is complete.*

The clinical data will be stored in the NEI's research database, the Clinical Research Information System (CRIS) and The Emmes Corporation's database. All individual data will remain confidential.

5.0 RISKS AND DISCOMFORTS

5.1 Risks and Discomforts Associated with the Clinical Assessments

The clinical visits will involve assessments that are commonly performed in the regular care of patients with RCD and ESCS.

1. Dilating drops may sting, cause an allergic reaction, precipitate an attack of angle closure glaucoma, worsen the participant's light sensitivity and distort near vision making tasks such as reading and computer work difficult. Vision typically returns to normal after two to four hours but, may be blurry up to 24 hours. Serious side effects (e.g., high blood pressure, confusion, hallucinations and seizures) are very rare and pupillary dilation is accepted as part of the standard of care for individuals with RCD and ESCS.
2. In rare instances, the cornea may be abraded during measurement of intra-ocular pressure or use of a contact lens (used for examination purpose only and not a contact lens used to correct one's refractive error). A corneal abrasion of this sort may be painful, but it heals quickly with no lasting effects.
3. The 3 mm punch skin biopsy can cause some post procedural pain and lead to limited scarring at the site of the biopsy.
4. Blood draws can cause discomfort and bleeding/bruising at the site of venous puncture. There is a remote risk of fainting or local infection. If any of these conditions arise, they will be treated.
5. The fluorescein dye used in fluorescein angiography can make a participant's skin turn yellow for several hours; also, the participant's urine will turn orange for up to 24 hours after the exam. Some participants may be slightly nauseated during the exam, but their nausea usually lasts only a few seconds. If the dye extravasates during the injection, the skin around the injection site may feel mildly uncomfortable or become yellow. In rare

cases, participants may have an allergic reaction to the dye. Participants with known allergies to the procedure are excluded from this study. Treatment typically consists of an oral antihistamine medication but may require intravenous antihistamine administration if the symptoms are severe. Very rarely will a participant experience anaphylaxis. This would be treated immediately by trained personnel with drugs or, if necessary, intubation.

6. The medical/ophthalmic history, microperimetry and physical examination entail no medical risk. No additional risks or discomforts are expected for the other clinical procedures.

theoretical discomforts of the investigational product include transient conjunctival edema or erythema. Other theoretical side effects may include intraocular inflammation, corneal toxicity and cataract. Possible discomforts associated with punctal pressure application include eye irritation and redness. Possible risks associated with eye drop administration include eye inflammation and infection if the dropperette tip becomes contaminated. This risk is reduced by using daily dropperettes for each set of instillations.

6.0 PARTICIPANT MONITORING

Participants will be monitored for adverse events over the course of the study by the study investigators. The principal investigator (PI) will be responsible for individual safety monitoring. Monitoring will be performed through interim systemic and ocular history, ophthalmic examination and assessment of the results of study examinations. In particular, the following adverse events will be closely monitored for safety:

1. Anterior surface injection/ocular erythema
2. Ocular inflammation
3. Increase or decrease in intraocular pressure
4. Formation of cataract or lenticular opacities
5. Development of CNV in the study eye, in which case it may be considered a safety event and treatment termination considered
6. Changes in visual function, different from those expected in the natural history of RCD or ESCS - (Adverse changes in visual function such as a decrease in visual acuity of > 0.3 logMAR from baseline).
7. Serious adverse reactions where there is a reasonable possibility that the IP caused the event

6.1 Participant Withdrawal Criteria

Participants may choose to withdraw from this study for any reason at any time without penalty or prohibition from enrolling in other clinical protocols. Investigators may withdraw a participant from study participation if a new health condition becomes evident that requires care proscribed by the protocol. Investigators may also withdraw a participant if s/he experiences a serious adverse reaction.

6.2 Reporting of Pregnancy

If the staff becomes aware that a female study participant has become pregnant during the study, investigational product will be discontinued. The investigator and participant will determine whether to continue any remaining study visits or to exit the study.

If the staff becomes aware that a male study participant impregnates his partner during the study, the investigator will remind the participant of the potential risks to the unborn fetus.

In either case of reported pregnancy, participant (or partner) will be referred to the NIH OB/GYN consultation service for evaluation and counseling. The investigator must follow the participant (or partner) until the pregnancy outcome.

7.0 OUTCOME MEASURES

7.1 Primary Outcome Measures

The primary outcome measure related to the safety and tolerability of IFN gamma-1b administered topically at the prescribed dosage for macular cystic changes in participants with RCD and ESCS will be assessed by the number and severity of adverse events related to the IP and the number of withdrawals.

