Design: This is a single-center, prospective, uncontrolled, unmasked pilot Phase I/II study of the safety, tolerability and possible efficacy of IFN gamma-1b in participants with RCD and ESCS and macular cystic changes. One eye of up to five participants with RCD with significant macular cystic changes and up to five participants with ESCS with significant macular cystic changes [evidenced by optical coherence tomography (OCT) >275 microns central macular thickness and/or disruption of foveal contour] will receive topical IFN gamma-1b instilled as drops on the cornea. The initial stage of the study will include two participants from each disease category. Once all four participants have completed the 8-week visit, enrollment will be halted. Safety Adverse Event Review Committee members unaffiliated with the study will review the

data as a preliminary assessment of safety and efficacy and to determine whether enrollment should continue. If the committee determines enrollment will continue, three additional participants with RCD and three participants with ESCS will be enrolled. The study will be completed once the final participant has received one year of follow-up.

Outcome Measures: The primary outcome measure related to the safety and tolerability of IFN gamma-1b administered topically at the prescribed dosage for macular cystic changes in participants with RCD and ESCS will be assessed by the number and severity of adverse events related to the IP and the number of withdrawals at 52 weeks (one year) post-administration. Additional safety of IFN gamma-1b administered topically in participants with RCD and ESCS will be determined from the assessment of retinal function, ocular structure and occurrence of adverse events at all time points. Secondary outcomes include changes in visual function including visual acuity and microperimetry, and retinal imaging with OCT and fluorescein angiography.

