4.4 Study Visits

Participants receiving IP will be provided with on-campus lodging for the first three days to complete the baseline assessments and for frequent monitoring to ensure good compliance and correct eye drop instillation technique (Days 1, 2 and 3). Scheduled clinic visits will occur at baseline, Days 1, 2 and 3, and Weeks 2, 5 and 8. A 52-week (one year) safety visit may be conducted at the NIH (on site) or with a local ophthalmologist (if the participant is unable/unwilling to come to NIH). Although there may be differences in testing among the various private physicians, at a minimum, all participants receiving IP must provide documentation of the assessments noted in Week 52 on the study flowsheet. After the participant signs a release of information with his/her ophthalmologist, the examination results will be sent to NEI. NEI will pay for the costs associated with obtaining medical records.

In addition, one of the investigators will conduct a phone interview with participants receiving IP at Weeks 1 and 6 to inquire about ocular complications. One or more unscheduled visits for safety assessment can be added based on the discretion of the investigators.

The regimen of IFN gamma-1b administration will consist of two weeks of therapy, dosing the study eye four times daily, with each dose consisting of a four-drop series, each drop spaced by 5 minutes, for a total of 16 drops delivered per day. The daily dose of IFN gamma-1b will be 112 µg topically (7 µg per drop, applied in 16 drops). Punctal occlusion will be employed to reduce systemic absorption. Investigators will train participants receiving IP on proper drop administration and monitor participants during the initial visits.

If at any time during the study participants experience ocular redness or other ocular concerns, they will be evaluated as soon as possible and the investigator may choose to terminate or reduce the dosage of the IFN gamma-1b eye drops. The dosage may be reduced to a three-drop series four times daily if symptomatic ocular surface disease and/or red eye develops.

Participants receiving IP may be restarted on the drops if the ocular condition resolves, at the investigator's and participant's discretion. Follow-up visits to manage ocular complications will be arranged, independent of and in addition to the prescribed visit schedule of the protocol.

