4.5.3 Preparation and Administration

Commercially-available Actimmune[®], manufactured by Horizon Pharma, will be used in this study and provided to the NIH CC Pharmacy. Vials of Actimmune[®] will be placed in a 2-8° C (36-46° F) refrigerator immediately upon receipt to ensure optimal retention of physical and biochemical integrity. The vials will not be frozen. Excessive or vigorous agitation will be avoided and the vials will not be shaken. The vials will be shipped from the NIH CC Pharmacy under controlled conditions to Pine Pharmaceuticals ([name]) to be re-packaged into single daily use 1 mL dropper bottles. IFN gamma-1b will be supplied to participants in the re-packaged single daily-use dropperettes to be stored in a 2-8° C (36-46° F) refrigerator. A single dropperette contains 1 mL of IFN gamma-1b (Actimmune[®]) at a

concentration of 200 µg/mL, which is equivalent to 28 drops. Each drop provides a dose of 7 µg of investigational product. Between daily uses, participants will store the open dropperette in the refrigerator or in a cooler with a cold pack at 2-8° C. Participants will be given cooler bags for transporting dropperettes. Once opened, each dropperette should be discarded within 24 hours. Participants will be given containers for disposal of the used dropperettes.

Participants will use a new dropperette each day as instructed from the Day 1 visit through the day prior to the Week 2 visit (see Appendix 2). Administration of topical IFN gamma-1b drops should be spaced throughout the day (approximately at breakfast, lunch, dinner and bedtime depending upon the dosage received) as instructed. Participants will be instructed to immediately discard dropperettes after each day's use in the provided disposal container which will be returned to the clinic at their next visit. Participants will be instructed on the proper administration techniques during their initial visit.

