8.1 Analysis

All reported adverse events will be tabulated and presented by system organ class, severity and relationship to study therapy.

Secondary outcomes will be presented for each participant and tabulated over time, as described in Section 7.2. Additionally, these outcomes will compare the changes within the study eye from baseline and the changes between the study eye and control eye over time.

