13.2 NEI Serious Adverse Event Review Committee

The NEI Serious Adverse Event Review Committee, which consists of the NEI Clinical Director and three other NEI physicians, will be responsible for reviewing any reported serious safety events, if they occur under this protocol. The Committee will review accumulating data on a semiannual basis to determine whether the study should continue. If changes to the protocol are indicated, recommendations will be made to the NEI Director and IRB who will consider and act on such recommendations in a timely manner. Should any serious suspected adverse reactions occur, the NEI Clinical Director may, at his discretion, assemble the Review Committee before the scheduled date to consider whether the study should move forward. The Review Committee or Principal Investigator can stop the study at any time if it appears there are any unexpected serious suspected adverse reactions that would outweigh any potential benefits of treatment. In addition, if three or more participants experience non-serious suspected adverse reactions that require temporary or permanent cessation of the investigational product, the Principal Investigator shall report this to the NEI Clinical Director. The NEI Clinical Director may convene the Review Committee before the scheduled time to consider the cessation of the study as a whole. The NEI Serious Adverse Event Review Committee or IRB may recommend temporarily suspending or closing enrollment, or stopping the study at any time due to safety concerns, demonstration of efficacy or lack of efficacy or slow recruitment.

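### The withdrawal count in the primary measure fits a two-week regimen poorly: it runs for 52 weeks, counts departures for any reason, and leaves out participants who reduce, interrupt or stop the drops but stay in follow-up

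*Combined protocol and SAP*

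**What the plan says.** **Outcome.** Section 7.1 (Primary Outcome Measures) assesses safety and tolerability at the prescribed dose by "the number and severity of adverse events related to the IP and the number of withdrawals". It gives no time frame and does not define withdrawal. The précis, under Outcome Measures, supplies the time frame: "the number of withdrawals at 52 weeks (one year) post-administration".

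**Treatment.** Section 4.4 (Study Visits) states: "The regimen of IFN gamma-1b administration will consist of two weeks of therapy". Section 4.5.3 has participants use a new dropperette daily "from the Day 1 visit through the day prior to the Week 2 visit".

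**Dose changes.** For redness or other ocular concerns, section 4.4 says "the investigator may choose to terminate or reduce the dosage of the IFN gamma-1b eye drops". It adds: "The dosage may be reduced to a three-drop series four times daily if symptomatic ocular surface disease and/or red eye develops". Drops may be restarted once the condition resolves.

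**Follow-up and withdrawal.** Section 4.1 follows everyone who receives the product for 52 weeks. Section 6.1 describes withdrawal as leaving the study, which a participant may do at any time and for any reason. Section 6.2, on pregnancy, treats stopping the product and leaving the study as two separate decisions.

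**Analysis.** Section 8.1 says: "All reported adverse events will be tabulated and presented by system organ class, severity and relationship to study therapy". Neither 7.1 nor 8.1 names reduction, interruption or discontinuation of the drops.

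**Replacement.** Section 3.0 allows up to two further participants to be enrolled, to reach five per disease group in the primary analysis, if anyone withdraws before five days of treatment.

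**The concern.** Tolerability of a two-week eye-drop regimen is mainly a question of whether participants could take it as prescribed. The protocol's own response to poor ocular tolerance is to reduce or stop the drops, not to remove the participant from the study. A count of study withdrawals does not register that response. It does register departures in the long off-drug period that have nothing to do with the product.

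The adverse event tables fill only part of the gap. They are laid out by system organ class, severity and relationship. A mild, related red eye that ended dosing would look the same there as one in a participant who took all 16 drops a day throughout. A participant who stops without a reported event appears in neither component.

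The replacement rule adds to this. If participants who leave before five days are left out of the primary analysis, as the wording of section 3.0 suggests, early departures caused by the drops could be missing from the one count meant to show them.

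At stake is how the tolerability result can be read. A low withdrawal count would not show that the regimen could be taken, and a raised one would not show that it could not.

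**Working it through.** The plan states no sample size calculation, event rate or power, so there is no such figure to reproduce. Its daily dose does check: 4 doses × 4 drops × 7 µg = 112 µg, as in section 4.4. The reduced regimen is 4 × 3 × 7 = 84 µg, and 84/112 = 75%.

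**1. Share of the withdrawal window on drug**

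Inputs: two weeks of therapy (4.4); Week 52 target at day 365 and a Week 2 window of ±5 days (Appendix 1); dosing from Day 1 to the day before the Week 2 visit (4.5.3).

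- Two weeks: 14/365 = 3.8% on drug, so 351/365 = 96.2% off drug.
- Section 4.5.3 rule at the target date: 13/365 = 3.6% on drug.
- Section 4.5.3 rule across the Week 2 window: 8/365 = 2.2% to 18/365 = 4.9% on drug.

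The off-drug share is 95% to 98% on any of these counts.

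**2. What the withdrawal count can miss**

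The documents give no intolerance rate, so the rates here are assumptions. Let n = 10, p = the chance that a participant reduces or stops the drops, and q = the share of those who also leave the study. Participants are taken as independent.

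- P(at least one reduces or stops) = 1 − (1 − p)^10
- P(no withdrawal due to intolerance) = (1 − pq)^10

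| p | P(at least one reduces or stops) | P(no such withdrawal), q = 0 | q = 0.25 | q = 0.5 |
|---|---|---|---|---|
| 0.1 | 0.65 | 1.00 | 0.78 | 0.60 |
| 0.2 | 0.89 | 1.00 | 0.60 | 0.35 |
| 0.3 | 0.97 | 1.00 | 0.46 | 0.20 |

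At p = 0.3, three participants are expected to reduce or stop. Expected withdrawals for that reason are 10 × 0.3 × q, which is 0, 0.75 or 1.5.

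As a single example, suppose 4 of 10 reduce or stop and all stay in follow-up. The withdrawal component reads 0/10 (exact 95% interval 0 to 31%), while the count of affected participants is 4/10 (12 to 74%). This illustrates the withdrawal component only.

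**3. What the withdrawal count can add**

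Let r be an assumed one-year risk of leaving for unrelated reasons. P(at least one among 10) = 1 − (1 − r)^10, which is 0.40, 0.65 and 0.89 for r = 5%, 10% and 20%. If such departures were spread evenly over the year, about 96% of them would fall after dosing.

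**The case against.** A reader might infer that the primary measure misses drug intolerance altogether. The documents do not support that. Section 7.1 names related adverse events before withdrawals. Ocular surface injection and inflammation head the list of closely monitored events in section 6.0, and section 8.1 tabulates events by severity and relationship. The redness behind a dose reduction should therefore reach the primary measure. In the example above, the plan would report those events alongside the 0/10, not the 0/10 alone.

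Other points on the same side:

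- No threshold, test or continuation rule rests on the withdrawal count, and section 8.0 makes the analysis descriptive and by participant. This stands, and it limits the consequences.
- Section 13.2 already requires a report when three or more participants have "non-serious suspected adverse reactions that require temporary or permanent cessation of the investigational product". This mitigates the gap, but it is an oversight trigger: it needs three cases, leaves out reductions and does not feed the outcome.
- The diary under section 4.5.4 records missed and low doses, so much of the information will exist. It is not named as an outcome.
- A year of follow-up is reasonable for delayed harms such as cataract. That supports the window for adverse events, but not for judging tolerability by withdrawals.

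Two further inferences go too far. Section 8.1 does not say that events on the full and reduced regimens will be merged, or that the two eyes will be merged; it is silent. Nor is the fellow eye unused: section 8.1 compares the eyes over time on the section 7.2 outcomes, and those comparisons could also show harm. Recording the eye and the action taken for each event is a reporting improvement, not the correction of a stated error.

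**Conclusion.** The point holds for the withdrawal component of the primary measure. That component counts leaving the study for any reason over a window that is about 96% off drug, and it leaves out reduction, interruption and stopping of drops by participants who remain in follow-up. The gap in the measure as a whole is narrower: the dosing consequence of an adverse event, and any stopping without a reported event.

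The 96% follows from the documents' own durations. The 52-week frame comes from the précis, not from section 7.1. That a participant who stops the drops stays in follow-up is inferred from sections 4.1, 4.4, 6.1 and 6.2 read together; no rule says so outright. That early leavers drop out of the primary analysis is likewise a reading of section 3.0. The probabilities rest on assumed rates and show direction and possible size only.

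This is a matter of outcome definition. No sample size or error rate changes. It is worth settling before analysis because it concerns the primary question and costs little.

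**What to change.** **Section 7.1**

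- Define withdrawal as leaving the study, and state the 52-week time frame there.
- Add as the tolerability measure the number of participants with an adverse-event-driven reduction, interruption or permanent discontinuation of the product during the dosing period. The denominator is everyone who received any dose, including anyone replaced before five days of treatment.
- Report study withdrawals separately, with the reason and whether the participant was on or off drug.
- List separately any participant who stopped or reduced drops without a reported adverse event.

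**Section 8.1**

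- For each ocular adverse event, list the affected eye and the action taken with the product.

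The cost is wording in two sections and one extra table. The diary covers drops, days and times, but a field for the reason may be needed; the adverse event form is not in the documents, so what it already collects cannot be confirmed. The tolerability figure may look less favourable than a withdrawal count would. No dosing, stopping or restart rule is changed.
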